6.1.4. Handling of Dropouts or Missing Data

Data will be included in the analysis according to the analysis visit windows described in Section 6.1.5.

Treatment of intercurrent events (ICEs) will be as described in Table 3. Briefly, subjects who withdraw from the study after treatment begins will be encouraged to complete an Early Termination Visit where all Visit 6 assessments will be performed. If the subject is lost to follow-up or otherwise unable to complete the Visit 6 assessments or if the subject uses a prohibited medication prior to the planned end of treatment, the Visit 6 HAM-A score will be set to missing. If the fraction of missing change from baseline to Visit 6 HAM-A total scores in the ITT population is ≤ 0.05 , missing change scores will be imputed with treatment group mean change scores for the primary efficacy analysis. If the fraction of missing change scores is greater than 0.05, multiple imputation of the change from baseline to Visit 6 HAM-A total scores will be carried out for the primary efficacy analysis. The fraction of missing change from baseline to Visit 6 HAM-A total scores will be computed as described in Section 6.1.7.2. The multiple imputation procedure will not impute individual HAM-A item scores or HAM-A total scores; only change from baseline to Visit 6 HAM-A total scores will be imputed. Other efficacy and safety data will not be imputed and will be analyzed as observed.

Table 3: Strategies for Intercurrent Events

ICE	Strategy for Addressing ICE
Treatment discontinuation following randomization but prior to Week 4.	While on Treatment Strategy The research objectives seek to understand the response to PH94B compared to placebo while subjects are actively using the study medication. Subjects who discontinue will undergo an Early Termination Visit and provide all Visit 6 outcome measures and safety assessments for the efficacy analysis.

ICE	Strategy for Addressing ICE

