
Treatment discontinuation following randomization but prior to Week 4 (subject lost to follow-up).
	
Hypothetical Strategy Measurement following ICE is unavailable and will be considered missing. Multiple imputation of the change from baseline to Visit 6 HAM-A scores will be carried out for the primary efficacy analysis using important subject variables and treatment assignment, if the fraction of missing change from baseline to Visit 6 HAM-A scores in the ITT population is greater than 0.05. In addition, the primary efficacy measure will be subjected to sensitivity analysis (complete case comparison and control-case using mean change from baseline HAM-A from the placebo group).

Use of prohibited medication prior to Week 4.
	
Hypothetical Strategy Measurement following ICE is not of interest and will be considered missing. Multiple imputation of the change from baseline to Visit 6 HAM-A scores will be carried out for the primary efficacy analysis using important subject variables and treatment assignment, if the fraction of missing change from baseline to Visit 6 HAM-A scores in the ITT population is greater than 0.05. In addition, the primary efficacy measure will be subjected to sensitivity analyses (complete case comparison and control-case using mean change from baseline HAM-A from the placebo group).

Abbreviations: HAM-A = Hamilton Anxiety Scale; ICE = intercurrent event.

The imputation approach has 2 broad components: i) the multiple imputation process for the placebo and PH94B data; and ii) the analysis method that will be used to draw inference regarding the primary estimand (Table 4), along with the method for combining the results across the multiply-imputed datasets. The primary estimand is defined in Section 8.1.

The imputation for the primary efficacy endpoint will be carried out in SAS using the fully conditional specification (FCS) method with a regression model approach (Carpenter and Kenward, 2013). The method assumes data are missing at random (MAR). Thus, subjects with missing values will have imputed values similar to other subjects with comparable observed profiles in the regression variables. The imputation will be carried out separately within each

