8.1. Primary Efficacy Analysis

The primary endpoint will be tested for the following hypothesis:

H₁₀: Mean change in HAM-A total score from Visit 2 (Baseline) to Visit 6 does not differ between PH94B and placebo.

H₁₁: Mean change in HAM-A total score from Visit 2 (Baseline) to Visit 6 does differ between PH94B and placebo.

The estimand for the primary efficacy endpoint has the following components:

Table 4: Primary Efficacy Estimand

Attribute	Definition
Treatment	The treatment of interest is PH94B, 3.2 µg administered as an intranasal solution [REDACTED]. The active drug will be compared to a placebo control.
Population	The population of interest is adults with AjDA as defined by inclusion and exclusion criteria.
Variable of Interest	The variable of interest is change in subject reported severity of anxiety as measured by change from baseline in HAM-A total score using the SIGH-A, after 4 weeks of randomized treatment with study drug.
Intercurrent Events	Treatment discontinuation prior to the planned assessment time frame. Intercurrent events will be treated as described in Table 3.
Population Summary	The difference in change from baseline in mean HAM-A total score between PH94B-treated and placebo-treated subjects after 4 weeks of treatment.

Descriptive summaries of HAM-A total scores and change from baseline in HAM-A total scores will be provided for the primary endpoint by visit and by treatment group, based on the observed data.

An ANCOVA model with change from baseline to Visit 6 in HAM-A total scores as the outcome, treatment group as the factor, and baseline HAM-A as a covariate will be used to test the null hypothesis that there is no difference between PH94B- and placebo-treated subjects in mean change from baseline to Visit 6 in HAM-A total score. The analysis will be performed in the ITT population using SAS PROC MIXED. The following parameters will be presented: the change from baseline LS means and standard error (SE), 95% CI for the LS means, *p* value for testing if the LS mean is different than 0, LS mean difference between treatment groups (PH94B minus placebo) with SE, 95% CI for the LS mean difference, and *p* value for testing if the treatment LS means are equal.

If, for unanticipated reasons (intercurrent events), the fraction of subjects with missing change

AD-ST-33.06 Effective date: 12-Nov-2020

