8.2. Secondary Efficacy Analyses

8.2.1. Analysis of Proportion of CGI-I Responders

The CGI-I secondary endpoint will be tested for the following hypothesis:

H_{20} : The proportion of CGI-I responders at Visit 6 does not differ between PH94B and placebo.

H_{21} : The proportion of CGI-I responders at Visit 6 does differ between PH94B and placebo.

The estimand for the CGI-I secondary efficacy endpoint includes the same population, treatment, and anticipated intercurrent events as the primary estimand. The variable of interest is the proportion of CGI-I responders at Visit 6. The proportion of CGI-I responders will be calculated as described in Section 6.1.7.3. The population-level summary measure is the difference in the proportion of CGI-I responders between PH94B-treated and placebo-treated subjects at Visit 6.

The PH94B and placebo proportions of CGI-I responders will be compared using a normal approximation (Wald) test for the difference between 2 binomial proportions. If expected cell sizes are less than 5, a Fisher's exact test will be used. The analysis will be performed using the ITT population. The following parameters will be presented: proportion of responders in each

treatment group, odds ratio and corresponding 95% CIs for PH49B responders versus placebo responders, and *P* value for the Wald test for equality of proportions will be presented.

Additionally, CGI-I scores and responder status will be summarized using frequencies and percentages by visit and by treatment group.

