8.2.2. Analysis of the Proportion of PGI-C Responders

The PGI-C secondary endpoint will be tested for the following hypothesis:

H₃₀: The proportion of PGI-C responders at Visit 6 does not differ between PH94B and placebo.

H₃₁: The proportion of PGI-C responders at Visit 6 does differ between PH94B and placebo.

The estimand for the PGI-C secondary efficacy endpoint includes the same population, treatment, and anticipated intercurrent events as the primary estimand. The variable of interest is the proportion of PGI-C responders at Visit 6. The proportion of PGI-C responders will be calculated as described in Section 6.1.7.4. The population-level summary measure is the difference in the proportion of PGI-C responders between PH94B-treated and placebo-treated subjects at Visit 6.

The analysis for this endpoint will be exactly parallel to the one described for the CGI-I secondary endpoint in Section 8.2.1.

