8.2.3. Secondary Efficacy Analysis of Change from Baseline in ADNM Total Score

The ADNM secondary endpoint will be tested for the following hypothesis:

H₁₀: Mean change in ADNM total score from Visit 2 (Baseline) to Visit 6 does not differ between PH94B and placebo.

H₁₁: Mean change in ADNM total score from Visit 2 (Baseline) to Visit 6 does differ between PH94B and placebo.

The estimand for the ADNM secondary efficacy endpoint is the same as that for the primary endpoint, except that it uses the ADNM total scores as the variable of interest. Change from baseline to Visit 6 in ADNM total score will be analyzed analogously to the primary endpoint. Multiple imputation will not be performed.

Descriptive summaries will be provided for observed ADNM total scores and changes from baseline by visit and by treatment group.

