8.2.4. Secondary Efficacy Analysis of Change from Baseline in IADQ Total Score

The IADQ secondary endpoint will be tested for the following hypothesis:

H₁₀: Mean change in IADQ total score from Visit 2 (Baseline) to Visit 6 does not differ

between PH94B and placebo.

H₁₁: Mean change in IADQ total score from Visit 2 (Baseline) to Visit 6 does differ between PH94B and placebo.

The estimand for the IADQ secondary efficacy endpoint is the same as that for the primary endpoint, except that it uses the IADQ total scores as the variable of interest. Change from baseline to Visit 6 in IADQ total score will be analyzed analogously to the primary endpoint. Multiple imputation will not be performed.

Descriptive summaries will be provided for observed IADQ total scores and changes from baseline by visit and by treatment group.

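### After prohibited medication, SAP 6.1.4 sets only the Visit 6 HAM-A to missing, although the secondary endpoints adopt the primary estimand or its intercurrent events

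*SAP*

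**What the plan says.** SAP Table 3 assigns use of prohibited medication before Week 4 to a hypothetical strategy: "Measurement following ICE is not of interest and will be considered missing". That sentence is not limited to one scale; the imputation described after it covers the HAM-A change only. Table 4, the primary estimand, names treatment discontinuation as the intercurrent event and then refers onward: "Intercurrent events will be treated as described in Table 3". Prohibited medication enters the primary estimand by that route.

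The secondary endpoints attach themselves to this framework in two ways.

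- **ADNM and IADQ** (SAP 8.2.3, 8.2.4) take over the whole estimand except the variable: "The estimand for the ADNM secondary efficacy endpoint is the same as that for the primary endpoint", and "The estimand for the IADQ secondary efficacy endpoint is the same as that for the primary endpoint".
- **CGI-I and PGI-C** (SAP 8.2.1, 8.2.2) take over part of it. The CGI-I estimand "includes the same population, treatment, and anticipated intercurrent events as the primary estimand", and 8.2.2 says the same for PGI-C. Each has its own variable and summary measure.

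The data rule is in SAP 6.1.4: "if the subject uses a prohibited medication prior to the planned end of treatment, the Visit 6 HAM-A score will be set to missing". The same paragraph ends: "Other efficacy and safety data will not be imputed and will be analyzed as observed".

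**The concern.** An estimand fixes what happens to data collected after an intercurrent event. Here the stated strategy is hypothetical, but the data rule carries it out for one score only. If a subject takes a prohibited drug and is then seen at Visit 6, the HAM-A from that visit is removed. The CGI-I, PGI-C, ADNM and IADQ from the same visit stay in.

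For CGI-I and PGI-C, a rating of much or very much improved then counts as a response. For ADNM and IADQ, the score enters the ANCOVA as an ordinary change from baseline. In effect the secondary analyses would follow a treatment-policy strategy for this event while their text points to a hypothetical one. A secondary result could then differ from the primary result for this reason alone. The SAP says its tests will inform Phase 2b and Phase 3 planning, so it should be clear what each one estimates.

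**Working it through.** This is mainly a question of consistency, so the provisions are set side by side first.

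| Place | Provision on scores after prohibited medication |
|---|---|
| SAP Table 3 | Considered missing, no scale named; imputation for HAM-A change only |
| SAP 6.1.4 text | Visit 6 HAM-A set to missing; other efficacy data as observed |
| SAP 6.1.7.3, 6.1.7.4 | Responder is a score of 1 or 2; denominator is subjects with a non-missing score; no condition on prohibited medication |
| SAP shell, Table 14.2.2.1 | Visit 6 includes completers and early-termination visits; no exclusion for prohibited medication |
| SAP 8.2.3, 8.2.4 | Same estimand as the primary; no multiple imputation; no set-to-missing step |
| Protocol Table 13-1 | Post-event measurement missing; multiple imputation planned for Visit 6 efficacy measures in general |
| SAP section 11 | Does not list the narrowing from efficacy measures in general to HAM-A |

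**Can such scores exist?** Yes. Protocol 8.3 gives the investigator the right to withdraw a subject who needs a prohibited medication, but does not make withdrawal automatic. It also asks subjects who discontinue early to return for the weekly visits or for the Visit 6 assessments.

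**What one subject is worth.** The documents give no rate of prohibited-medication use and no figure of their own to reproduce. The inputs are 40 subjects randomised 1:1 (Protocol synopsis), taken as 20 per arm, and a two-sided 0.05 level (SAP 4.1). Suppose an arm has x responders out of 20 and one of them used a prohibited drug.

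- Recounted as a non-responder: x/20 − (x − 1)/20 = 1/20 = 5.0 points.
- Set to missing: x/20 − (x − 1)/19 = (20 − x)/380. For x = 7 this is 13/380 = 3.4 points; for x = 15 it is 5/380 = 1.3 points. It equals 5.0 points only when x = 1.

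**Illustration with assumed counts.** The test is the unpooled Wald test, z = (p1 − p2) / √[p1(1 − p1)/n1 + p2(1 − p2)/n2]. As a check on the formula, 34/45 against 17/46 gives z = 4.03, which matches the value in Protocol 5.2.2. For 13/20 against 7/20, z = 0.30/√(2 × 0.65 × 0.35/20) = 0.30/0.151 = 1.99, p = 0.0467.

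| Assumed result, PH94B vs placebo | Responders who used a prohibited drug | As observed | Set to missing | Non-responder |
|---|---|---|---|---|
| 15/20 vs 7/20 | 2 on placebo | 40.0 points, p = 0.0055 | 15/20 vs 5/18: 47.2, p = 0.0010 | 15/20 vs 5/20: 50.0, p = 0.0003 |
| 15/20 vs 7/20 | 2 on PH94B | 40.0 points, p = 0.0055 | 13/18 vs 7/20: 37.2, p = 0.0131 | 13/20 vs 7/20: 30.0, p = 0.0467 |
| 13/20 vs 7/20 | 1 on PH94B | 30.0 points, p = 0.0467 | 12/19 vs 7/20: 28.2, p = 0.0669 | 12/20 vs 7/20: 25.0, p = 0.1020 |

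In these cases the handling moves the difference by about 2 to 10 points, in a direction set by the arm. In the borderline case it moves p across 0.05.

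**The case against.** The best reply is that Table 3 governs. SAP 6.1.4 refers intercurrent events to Table 3 and introduces its own account as a brief summary. Table 3 does not limit the missing-data sentence to HAM-A. The as-observed sentence closes a paragraph about imputation, so it may mean only that missing secondary scores stay missing. The non-missing denominators in 6.1.7.3 and 6.1.7.4, and the statement in 8.2.3 and 8.2.4 that multiple imputation will not be performed, fit that reading. On it, a user's CGI-I is missing and is not a response.

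That reading is possible, and for that reason the point is put as a natural reading and, at the least, a conflict. It is not the more natural one. The specific rule names HAM-A alone, and no secondary section, derivation or responder shell sets anything to missing. Two programmers could derive different responder counts from the same text.

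A second reply is that CGI-I and PGI-C do not claim the primary estimand. That is right. They share its population, treatment and anticipated intercurrent events, and Table 4 names only treatment discontinuation before pointing to Table 3. The full claim is made for ADNM and IADQ alone. The shared intercurrent events are, however, the part that matters here.

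A third reply is that the study is exploratory and its secondary tests are unadjusted for multiplicity. This lowers the stakes but does not settle which analysis is meant.

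**Conclusion.** The point holds. Followed as worded, SAP 6.1.4 produces secondary results that do not match the handling of prohibited medication that 8.2.1 to 8.2.4 adopt from the primary estimand. The primary analysis is not affected.

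The size is unknown. The 5 points per recounted responder assumes 20 analysed subjects per arm, and the tabulated counts are illustrations. If nobody uses a prohibited drug, the effect is zero.

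A reader might infer three stronger things that the documents do not support.

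- **A known direction of bias**, on the idea that prohibited use will be commoner in the less effective arm. No passage gives a rate or an arm. The prohibited list in Protocol 9.7.2 also includes centrally acting drugs for pain and muscle spasm, so use need not signal poor anxiety control. As-observed handling understates the responder difference if responding users are on placebo, and overstates it if they are on PH94B.
- **The same inconsistency in the HAM-A at Visits 3 to 5.** SAP 8.3 presents that as an exploratory analysis of observed data and claims no estimand for it.
- **That counting users as non-responders would restore agreement with Table 3.** It would not. That is a composite strategy, and in the second row of the illustration it gives 30.0 points against 37.2 for set-to-missing.

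**What to change.** Before the SAP is finalised and the data unblinded:

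1. In 6.1.4, extend the set-to-missing rule after prohibited-medication use to the Visit 6 CGI-I, PGI-C, ADNM and IADQ scores, and state that the remaining observed scores are analysed. This agrees with Table 3 and with the non-missing denominators in 6.1.7.3 and 6.1.7.4.
2. In section 11, list the departure from Protocol Table 13-1, which planned imputation for Visit 6 efficacy measures in general.
3. If as-observed analysis is preferred, remove the shared-estimand claim from 8.2.3 and 8.2.4 and the shared intercurrent-event claim from 8.2.1 and 8.2.2, and name a treatment-policy strategy for this event.
4. If non-responder counting is wanted, add it as a sensitivity analysis labelled as a composite strategy.

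The cost is a few sentences and one derivation flag, with no change to study conduct or data collection. The small downside of the first option is a few fewer observed secondary scores. It also rests on the assumption that the removed subjects would have resembled the others in their arm (for ADNM and IADQ, given baseline), and the SAP should say so.

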	
investigational product (IP) and will be dispensed a 1-week supply of PH94B or placebo. Subjects will then commence 4 weeks of double-blind treatment with the randomized IP 4 times per day.
 
Subjects will return for weekly site visits (Visits 3, 4, and 5), in which the subject will return the IP vials dispensed at the previous visit and receive new vials. Concomitant medications and adverse events (AEs) will be recorded. During these visits, the HAM-A, Patient Global Impression of Change (PGI-C), Clinical Global Impression - Improvement (CGI-I), CGI-S, and C-SSRS will be completed. Vital signs will be collected, and nasal passages will be examined.
 
When the subject returns for Visit 6, besides the assessments completed at Visits 3 through 5, the subjects will complete the MADRS, ADN, and IADQ; and have a physical examination, ECG, laboratory tests (chemistry and blood), urinalysis, urine drug screen, and urine pregnancy test conducted. Any remaining IP vials will be collected. The subject will then come back after a 1-week washout period for the Follow-up visit (Visit 7). During this visit, AEs and concomitant medications since the last visit will be collected and the HAM-A, C-SSRS, and the 20-item Physician Withdrawal Checklist (PWC-20) will be completed.
 
For each visit following Baseline (Visit 2), a \pm 2-day window will be allowed.
 
Safety considerations:
 
Safety and tolerability of PH94B will be assessed and summarized through changes from screening in clinical laboratory values, ECGs, physical examinations, and vital sign assessments following exposure to PH94B, as well as by comparison of AEs reported during treatment with the IP. To date, limited exposure to PH94B (<2 weeks, <4 doses per day) in over 200 subjects has resulted in no serious AEs (SAEs) and no AEs occurring with statistically greater frequency for the PH94B group than for the placebo group. In addition, the PWC-20 will be administered to document any withdrawal effects that may be occurring.

PLANNED NUMBER OF SUBJECTS	Forty adult subjects will be randomized 1:1 to PH94B or placebo.

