	
Interview Guide for the HAM-A (SIGH-A), after 4 weeks of randomized treatment with the study medication
 
4. Population-level summary measure: Difference in mean HAM-A total score between PH94B-treated and placebo-treated subjects after 4 weeks of treatment5. Anticipated intercurrent event: Treatment discontinuation prior to the planned assessment time frame
SAMPLE SIZE DETERMINATION	A sample size of 40 subjects was selected based on information from published studies on treatments for adjustment disorder suggesting that a clinically meaningful effect size could be estimated using a sample size of 40.
STUDY AND TREATMENT DURATION	
The sequence and maximum duration of the study periods will be as follows:
 
1. Screening and washout: [REDACTED]2. Treatment period: From Visit 2 (Baseline) through Visit 6 (End of Treatment)3. Follow-up period: Follow-up visit (Visit 7) conducted approximately 1 week after last treatment 
The maximum study duration for each subject is approximately 10 weeks.
 
The maximum treatment duration for each subject is 4 weeks.

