10.2.3 Treatment Period (Visits 3, 4, and 5)

At Visits 3, 4, and 5 the following assessments will be completed:

- Measure vital signs after the subject has rested for 5 minutes: seated systolic and diastolic blood pressure, heart rate, respiratory rate, and body temperature
- Perform clinical examination of both nasal passages
- Administer HAM-A
- Administer C-SSRS (since last visit)
- Administer CGI-S
- Administer CGI-I

- Administer PGI-C
- Returned vials dispensed at the previous visit and new vials will be weighed and dispensed (all weights will be documented in source documents and the eCRF)
- Record concomitant medication use
- Review and record AEs

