4.1. Introduction

Data processing, tabulation of descriptive statistics, calculation of inferential statistics, and graphical representations will primarily use Statistical Analysis System Software (SAS) (release 9.4 or higher). If the use of other software is warranted, the final SAP and the statistical methodology report will detail what software was used for what purposes.

Continuous (quantitative) variable summaries will include the number of subjects (n) with non-missing values, mean, SD, median, minimum, and maximum. The minimum and maximum will be reported with the same degree of precision (i.e., the same number of decimal places) as the observed data. Measures of location (mean and median) will be reported to 1 degree of precision more than the observed data and measures of spread (SD) will be reported to 2 degrees of precision more than the observed data.

Categorical (qualitative) variable summaries will include the frequency and percentage of subjects who are in the category or each possible value. The denominator for the percentage calculation will be based upon the total number of subjects in the study population for the treatment groups unless otherwise specified. Percentages will be presented to 1 decimal place. Counts of zero will be presented without percentages.

Unless otherwise indicated, all statistical tests will be conducted at the 0.05 significance level using 2-tailed tests, and p values will be reported. Corresponding 95% confidence intervals (CIs) will be presented for statistical tests. All p values will be displayed in four decimals and rounded using standard scientific notation (e.g., 0.XXXX). If a p value less than 0.0001 occurs it will be shown in tables as < 0.0001 ; similarly, if a p value greater than 0.9999 occurs, it will be shown in tables as > 0.9999 . Confidence intervals will be reported to 1 degree of precision more than the observed data.

This study is considered a Phase 2a exploratory study under an IND application for PH94B targeting AjDA. Statistical tests will be applied and interpreted to determine feasibility and best approaches for potential Phase 2b and Phase 3 studies.

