treatment group. The regression model will include the following variables: baseline HAM-A total score, sex, age, LSAS total score, and analysis site. For each imputation process, a total of 25 complete datasets will be created. The random seeds to be used in the imputation process are 813616018 for the PH94B treatment group and 80521516 for the placebo treatment group.

The analysis method for the multiple imputation will match that described for the primary efficacy analysis in Section 8.1. Results from the multiply-imputed datasets will be combined using the standard Rubin's rules for multiple imputation (Little and Rubin, 1987) and will be done in SAS using PROC MIANALYZE.

Two sensitivity analyses will be performed to assess robustness of the multiple imputation results to changes in missing data assumptions. The sensitivity analyses include 1) a complete case analysis where only subjects with non-missing change from baseline in HAM-A total scores will be included, and 2) a control-case analysis, where missing change from baseline in HAM-A total scores will be imputed by the mean change from baseline for the placebo group. Sensitivity analyses are detailed in Section 8.1.1.

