				Antisocial Personality Disorder: Lifetime	XXX
				Adjustment Disorder: Current	XXX
				Identify the Primary Diagnosis	XXXXXXXXXXXXXXXXXXXXXXXXXX

Abbreviations: DSM = Diagnostic and Statistical Manual of Mental Disorder; MINI = Mini International Neuropsychiatric Interview, SAD = Social Anxiety Disorder.
 Note: Study day is calculated relative to the date of first dose of study drug. The MINI was only collected at Visit 1 (Screening).

Programming Note: If MINI was not conducted, concatenate reason. Continue for remaining assessments. Do not include rater initials.

[figure not shown]
Listing 16.2.4.5 (cont.)
 Liebowitz Social Anxiety Scale (LSAS)
 All Subjects

Actual Treatment: XXXXXXX

Subject ID	LSAS Completed/ Reason Not Completed	Date/Time of Assessment (Study Day)	Score or Question	Result
XXXXX	Yes	DDMMYYYY:HHMM (XX)	20. Giving a report to a group: Fear or Anxiety 20. Giving a report to a group: Avoidance 21. Trying to pick up someone: Fear or Anxiety 21. Trying to pick up someone: Avoidance 22. Returning good to a store: Fear or Anxiety 22. Returning good to a store: Avoidance 23. Giving a party: Fear or Anxiety 23. Giving a party: Avoidance 24. Resisting a high pressure salesperson: Fear or Anxiety 24. Resisting a high pressure salesperson: Avoidance	X = XXXXXXXXXXXXX X = XXXXXXXXXXXXX

Abbreviations: LSAS = Liebowitz Social Anxiety Scale.
 Note: Study day is calculated relative to the date of first dose of study drug. The LSAS was only collected at Visit 1 (Screening).

Programming Note: If LSAS not completed, concatenate reason.

Listing 16.2.5.1
 Study Drug Dispensation
 All Subjects

Actual Treatment: XXXXXXXX

Subject ID	Study Visit [1]	Date/Time (Study Day)	Dispensing			Date/Time (Study Day)	Returning		
			Dispensed?/ Reason Not Dispensed	Vial 1 Dispensed?/ Kit Number/ Weight (g)	Vial 2 Dispensed?/ Kit Number/ Weight (g)		Returned?/ Reason Not Returned	Vial 1 Returned?/ Kit Number/ Weight (g)	Vial 2 Returned?/ Kit Number/ Weight (g)
XXXXX	XXXX	DDMMYYYY:HHMM (XX)	XXX	XXX/ XXXXXXX/ XX	XXX/ XXXXXXX/ XX				
	XXXX	DDMMYYYY:HHMM (XX)	XX/ XXXXXXXX			DDMMYYYY:HHMM (XX)	XXX	XXX/ XXXXXXX/ XX	XXX/ XXXXXXX/ XX
XXXXX	Visit 2 (Baseline)	DDMMYYYY:HHMM (XX)	XXX	XXX/ XXXXXXX/ XX	XX/ XXXXXXX/ XX				
	Visit 3	DDMMYYYY:HHMM (XX)	XXX	XXX/ XXXXXXX/ XX	XXX/ XXXXXXX/ XX	DDMMYYYY:HHMM (XX)	XX/ XXXXXXXX	XX	XXX/ XXXXXXX/ XX
	Visit 4	DDMMYYYY:HHMM (XX)	XXX	XXX/ XXXXXXX/ XX	XXX/ XXXXXXX/ XX	DDMMYYYY:HHMM (XX)	XXX	XXX/ XXXXXXX/ XX	XXX/ XXXXXXX/ XX

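### The imputation of missing Visit 6 HAM-A change ignores the Visit 3 to 5 scores, so a non-improver with no usable Visit 6 score is imputed much like a completer

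*SAP*

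**What the plan says.** SAP 6.1.4 and Table 3 treat the Visit 6 HAM-A as missing when a subject is lost to follow-up, cannot complete the Visit 6 assessments, or uses a prohibited medication. A subject who stops but attends an Early Termination visit contributes an observed score and is not imputed.

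The missing change score is then filled in by one of two rules:
- **More than 5% missing:** fully conditional specification multiple imputation with 25 datasets. "The imputation will be carried out separately within each" treatment group, and "The regression model will include the following variables: baseline HAM-A total score, sex, age, LSAS total score, and analysis site". The programming notes to Table 14.2.1.1 repeat this list.
- **5% or less missing:** the mean change of the subject's own arm.

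The SAP explains its missing-at-random assumption by saying that "subjects with missing values will have imputed values similar to other subjects with comparable observed profiles in the regression variables". It also restricts imputation to the Visit 6 change score.

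Protocol 10.2.3 lists "Administer HAM-A" at Visits 3, 4 and 5. The SAP uses those scores for visit summaries (8.1) and for an exploratory ANCOVA on observed data (8.3), but not for imputation. Protocol Table 13-1 speaks only of important subject variables and does not name predictors.

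Two sensitivity analyses are planned: complete case (SAP 8.1.1.1) and control-case, which inserts the placebo mean change (8.1.1.2). SAP 11 records that control-case replaces the zero-change analysis of Protocol Table 13-1.

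**The concern.** Every predictor in the model is fixed before the first dose. LSAS is no exception, since the listing shell notes that it is taken only at Screening. The comparable profiles on which the assumption rests therefore say nothing about how the subject responded. A subject lost in week 4 may have three on-treatment HAM-A scores showing no improvement, yet is imputed from the same distribution as a responder with the same baseline score, sex, age, LSAS and site.

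For a hypothetical strategy, the subject's own course before the event is the most direct evidence of where Visit 6 would have been. The plan expects some loss of this kind: its disposition table lists lack of efficacy as a reason for discontinuation, and Protocol 8.3 lists disease progression and need for a prohibited medication. If such loss is heavier in one arm, that arm's mean change looks too good and the primary comparison shifts with it.

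**Working it through.** **Inputs from the documents.** "Forty adult subjects will be randomized 1:1 to PH94B or placebo", so 20 per arm, and "all statistical tests will be conducted at the 0.05 significance level using 2-tailed tests". No SD, visit-to-visit correlation or dropout rate is visible, and Protocol 13.2 is redacted. There is no planned figure to reproduce, so every size below rests on stated assumptions.

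**1. Which rule applies.** With 40 in the ITT population, 2/40 = 0.050 gives arm-mean imputation and 3/40 = 0.075 gives multiple imputation. With 39, 2/39 = 0.051 would already give multiple imputation.

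**2. Formula.** Bias in an arm's mean = (fraction of the arm imputed) × (mean imputed change − true mean change of those subjects). Bias in the treatment difference = PH94B term − placebo term.

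**3. One arm, 20 subjects, 3 lost after Visit 5.** Assumed: SD of change 7; loss weight proportional to exp(k × standardized Visit 5 change), where worse change means likelier loss. At adjacent-week correlation 0.7 the planned model gives:

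| k | Bias in arm mean (points) |
|---|---|
| 0 (unrelated to response) | about 0 |
| 0.5 (weak) | −0.35 |
| 1.0 | −0.71 |
| 1.5 (strong) | −0.86 |

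Across correlations 0.6 to 0.8 the range is about −0.3 to −0.4 for weak selection and −0.8 to −1.0 for strong.

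**4. The same setting with Visits 3 to 5 in the model.** Bias is about 0 when loss depends only on recorded scores. If loss depends on the unseen Visit 6 score, about −0.7 remains (planned model about −1.3). Root-mean-square error of the arm mean falls by about 20 to 50%. Even with loss unrelated to response, it goes from 0.91 to 0.63 at correlation 0.7, a fall of 0.28/0.91 = 31%. With loss after Week 1 the gain is smaller: 0.92 to 0.77, or 0.15/0.92 = 16%.

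**5. The treatment difference.** Assumed: true changes −10 (PH94B) and −7 (placebo), residual SD 7, and loss after Week 2 strongly tied to poor Week 2 change. This is a large-sample calculation with sex, age, LSAS and site taken as non-prognostic.

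At correlation 0.8 with 20% lost on PH94B and 5% on placebo, PH94B dropouts stand at +1.0 at Week 2 and truly reach −5.1 at Week 4. They are imputed at −11.0, against −11.2 for completers.
- PH94B term: 0.20 × (−11.0 + 5.1) = −1.18.
- Estimated difference −3.83 against −3.00 true: net bias −0.83.
- Implied placebo term: −1.18 + 0.83 = −0.35.
- With weekly scores, dropouts are imputed at −5.2 and the difference is −3.01.

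| Lost, PH94B / placebo | Planned model, correlation 0.6 to 0.9 | True |
|---|---|---|
| 20% / 5% | −3.46 to −4.02 | about −3.0 |
| 15% / 5% | −3.32 to −3.73 | about −3.0 |
| 20% / 20% | −2.98 to −3.00 | about −3.0 |

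Equal loss gives no bias in the difference. By the formula, heavier loss on placebo reverses the sign.

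**6. No true effect, 20 per arm, correlation 0.8, 20% / 5% lost.** The planned model gives a mean difference of −0.84, against 0.05 with the Week 2 score in the model. False positives favouring PH94B are 4.2% against 2.4%. Total two-sided error is 5.1% against 4.4%.

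**7. The arm-mean rule.** Two lost in one arm is 10% of it. Using the step 5 assumptions at 10% loss, the bias is 0.10 × (−10.4 + 6.5) = −0.39 at correlation 0.6 and 0.10 × (−10.7 + 4.1) = −0.66 at 0.8. The flaw is the same, and single imputation also understates the variance.

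**The case against.** **Few subjects are affected.** Protocol 8.3 asks subjects who stop to keep their weekly visits or complete the Visit 6 assessments, with repeated contact attempts before they are declared lost. This stands and limits the scope. A reader might infer that everyone who leaves for lack of improvement is mis-imputed, but the documents confine imputation to those with no usable Visit 6 score.

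**Response-related loss is assumed.** Protocol 8.3 lists withdrawal reasons without frequencies, and some, such as intolerance, are not non-response. It is tempting to say that poor response is the usual reason for stopping, but nothing in the documents says so. If loss is unrelated to response, there is no bias, only avoidable imprecision.

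**The control-case analysis covers the direction that matters.** In part it does. It gives missing PH94B subjects the placebo mean, and in the step 5 example (20% / 5%, correlation 0.8) it returns −3.09 against −3.00 true. With equal 20% loss, however, it returns −2.39 against −2.98 true. It ignores each subject's own course and does not correct over-crediting of placebo dropouts. The complete-case analysis makes nearly the planned model's assumption and would not reveal the problem.

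**Twenty per arm is too few for more predictors.** This is fair against adding three scores to the five existing variables. It does not apply if the weekly scores replace three of them.

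**The study is an exploratory Phase 2a (SAP 4).** That lowers the stakes, but the change is nearly free.

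**Conclusion.** The concern holds. For subjects with no usable Visit 6 or Early Termination score, both imputation rules set aside on-treatment HAM-A scores that the trial already collects. If loss is related to poor response, non-improvers are imputed much like completers.

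The size depends wholly on assumed inputs. With 3 of 20 lost in one arm after Visit 5, the arm-mean bias runs from 0 to about −1.0 points, according to how strongly loss follows poor response. Bias in the treatment difference needs unequal loss of non-improvers.

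Two stronger readings are not supported. One is that the plan favours PH94B: the direction depends on which arm loses more non-improvers, and the documents do not say. The other is that weekly scores would remove the bias altogether: they do so only if loss depends on recorded scores, and a subject lost before Visit 3 has none to use. This is a change the sponsor should make before unblinding, not a defect that invalidates the primary analysis.

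**What to change.** Before unblinding, revise SAP 6.1.4 as follows:
- Multiply impute the missing Visit 6 change within arm from baseline HAM-A, analysis site (kept, as SAP 6.1.6 requires) and the Visit 3, 4 and 5 HAM-A scores. Visits 3 to 5 replace sex, age and LSAS, so the model still has five predictors.
- Impute sequentially, Visit 3 to Visit 6, so that subjects lost earlier contribute what they have.
- For prohibited-medication cases, use only scores from before the medication; set later ones to missing and impute them.
- Use the same model in place of arm-mean imputation when 5% or less is missing.

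Amend to match: the sentence in 6.1.4 restricting imputation to the Visit 6 change, Table 3, the threshold wording in 6.1.7.2 and 8.1, and the Table 14.2.1.1 programming notes. Protocol Table 13-1 names no predictors, so its wording on them can stay.

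The cost is minor SAP wording and a few lines of code, with no new data. The downside is that sex, age and LSAS leave the imputation model.
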